A second Phase II study called CHI-SQUARE, in patients with Acute Coronary Syndrome has also been completed. It was an ascending dose, placebo-controlled, double-blind, dose-response study that enrolled 507 patients (3:1 ratio active:placebo). The full study report is still in preparation; however, preliminary results indicate that CER-001 did not meet its primary endpoint of a reduction in total atheroma volume (TAV) as measured by IVUS for the 12 mg/kg CER-001 treated patients compared to the placebo patients. Methodological concerns regarding the IVUS analysis, as detected in the EXPRESS study, also pertain to CHI-SQUARE. An independent and blinded analysis of the IVUS images was conducted by a different IVUS core lab (SAHMRI, Adelaide Australia). In this post-hoc but blinded reanalysis, the 3 mg/kg treatment group showed consistent improvement relative to baseline and was numerically superior to placebo in all analysis populations. In the Modified Per Protocol analysis, statistical significance of 3 mg/kg over placebo was achieved for some of the IVUS measurements (7).

[figure not shown]

Figure 1. Change in IVUS parameters by treatment group and analysis population  
(LS Means from ANCOVA modeling with nonparametric testing due to non-normality of data; mITT = modified intent-to-treat, mPP = modified per-protocol population; PPP = per protocol population)

In general, CER-001 and placebo had a similar safety profile. The incidence and type of SAEs were similar for CER-001 and placebo, with the possible exception of infusion reactions (drug hypersensitivity reactions, anaphylaxis, and adverse drug reactions).

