## 5 RISK BENEFIT STATEMENT

All patients enrolled in this study will have four 3T-MRI measurements during a time period of 48 weeks. 3T-MRI is a non-invasive imaging technique that does not involve exposure to ionizing radiation. The magnetic field itself is not harmful; however, imbedded metallic fragments such as shrapnel or implanted medical devices that contain metal such as pacemakers may malfunction or cause problems during an MRI exam.

Patients in this study will have two FDG-PET scans during the study, the first one will be performed at baseline and the second and last assessment will be done at week 24. FDG-PET is routinely used in clinical practice. The total radiation exposure in the study corresponding to the two FDG-PET CT scans is 9.4 milli-Sievert. Labelled glucose, F-deoxyglucose, has no known side effects. No adverse effects are expected.

Two thirds of the patients randomized in the trial will receive twenty-nine infusions of CER-001 (8mg/kg) and one third will receive twenty-nine infusion of placebo. More than 400 patients have been exposed to CER-001 in previous clinical trials including 122 patients exposed to 12 mg/kg CER-001 in phase II study. Overall CER-001 has been well tolerated. The incidence and type of SAEs were similar for CER-001 and placebo, with the possible exception of infusion reactions which occurred more frequently with CER-001 and may occur more frequently at higher doses. These reactions were reversible in all cases and either resolved spontaneously or after management with antihistamines, steroids and/or IV fluids. A phase II study (CARAT) aiming to enroll 292 patients for evaluating the potential benefit of CER-001 in ACS patients is currently ongoing.

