#### **11.6 Expected Adverse Drug Reactions**

CER 001 has previously been administered to humans in single doses ranging from 0.25 to 45 mg/kg. No treatment related AE were reported in that single dose study. In the completed multiple dose studies the adverse event profile has been consistent with what would be expected from the experience of Phase I and Phase II studies and from treating these populations of patients.

AEs that would be reasonable to expect based on repeat dosing in animal toxicity studies include increased liver enzymes, and changes to red blood cell indices although these have not been observed with single or multiple human doses at a rate higher than that observed with placebo. Other AEs that may be anticipated are local injection site reactions and allergic responses. These reactions may include one or more of the following symptoms: wheezing, eye itching, eye swelling, facial swelling, rash, feeling cold, decrease in body temperature, cold sweat, cold shivers, chest pressure, chest pain, jaw pain, decreased blood pressure, increased blood pressure, fatigue, dizziness, headache, nausea, vomiting, stomach pains, and diarrhea.

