7.3.2 Treatment compliance

Treatment compliance will be assessed on the mITT population according to randomized treatment group. Compliance (%) with the study treatment will be summarized on each study period (Induction / Maintenance / Extension) and at W24, W48 as follows:

- Compliance during induction phase (%) = Number of infusions totally administered between W0 and W8 / 9 * 100
- Compliance during maintenance phase (%) = Number of infusions totally administered between W10 and W24 / 8* 100
- Compliance during extension phase(%) = Number of infusions totally administered between W26 and W48 / 12 * 100
- Compliance at W24 (%) = Number of infusions totally administered between W0 and W24 / 17
 * 100
- Compliance at W48 (%) = Number of infusions totally administered between W0 and W48 / 29* 100

Average dose, total dose of CER-001 as well as administered dose *vs* expected dose will be summarized at W8, W24, W48, and are defined as follows:

- Total dose at Wi (mg) = $\sum_{v=1}^{ni} CER001$ dose prescription for infusion $v\left(\frac{mg}{kg}\right)$ * Weight at infusion $v\left(kg\right)$ * Actual volume administered at infusion $v\left(mL\right)$ / 250, when n_i = number of infusions received between W0 and Wi
- Average dose at Wi (mg) = Total dose at Wi (mg) / number of infusions received between WO and Wi
- Administered dose vs expected dose at Wi (%) = Total dose at Wi (mg) / (8 * $\sum_{v=1}^{mi} Weight$ at infusion v) * 100, when m_i = number of infusions planned between W0 and Wi

In addition, a by-patient listing will be produced for each patient who verified for at least one visit:

- Dose prescription different from 8 mg/kg
- Time elapsed between study medication infusion preparation and study medication administration > 72h (48h for Canadian sites)
- Start infusion time stop infusion time > 65 min or < 55 min
- Total volume administered = No

For these patients, the listing will include, for all available visits:

- Patient ID, visit, treatment arm
- Dose prescription (mg/kg)
- Date and time of study medication infusion preparation
- Date of infusion, start and stop infusion time
- If not administered, reason
- If infusion duration different from 60 min, reason

CER-001-CLIN-009 CER-001

- Total volume administered (Yes/No)
- If No, volume administered (mL)

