7.5.1 Adverse events (AE)

AE term (Investigator term) will be assigned to the lowest level term (LLT), and a preferred term (PT) will be classified by a high level term (HLT), a high level group term (HLGT) and a system organ class (SOC) according to the Medical Dictionary for Regulatory Activities (MedDRA) thesaurus, version 19.1 or higher.

An adverse event will be considered as treatment-emergent (TEAE) if AE onset date is between first infusion of CER-001 and last infusion of CER-001 + 28 days, or if AE occurred before the first infusion of CER-001 but gets worse on study treatment. In case of incomplete date(s), see section 7.1.4.

An overview of the number of patients with at least one AE and the corresponding number of AEs will be presented including:

- Any AE
- Any TEAE
- Any serious TEAE
- Any severe TEAE
- Any TEAE leading to dose reduction of the study medication
- Any TEAE leading to temporary discontinuation of the study medication
- Any TEAE leading to permanent discontinuation of the study medication
- Any TEAE related to the study medication (Related = definite, probable or possible)
- Fatal AE
- Fatal TEAE
- Any coronary event (Coronary event = event for which HLGT = Coronary artery disorders)

All PT with HLGT = Coronary artery disorders will be described in the same way in a separate table.

CER-001-CLIN-009 CER-001

Note: recurring AEs (*i.e.* AEs classified with the same Preferred Term (PT)) for a given patient will be only counted once and only their most severe intensity or most severe relationship to the study medication will be described.

TEAEs will also be tabulated by System Organ Class (SOC) and PT. They will be presented according to seriousness (Serious / Not serious), severity (Mild/Moderate/Severe) and relationship with the study medication (Related / Not related). They will finally be tabulated by SOC and PT according to relationship with the study medication within severity.

The different analyses described above will be summarized overall, on the induction period and on the post-induction period (AEs that occurred during maintenance or extension phase). Assignment of AEs to periods will be performed as follows:

Period	Assignment
Induction	Start date of TEAE < date of infusion at W10
	(if day of AE is missing then impute to first of the month)
Post-induction	Start date of TEAE ≥ date of infusion at W10
	(if day of AE is missing then impute to first of the month)

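### No planned safety table counts the patients per arm with an infusion or hypersensitivity reaction, although the protocol says these reactions were more frequent with CER-001

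*SAP*

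**What the plan says.** **The risk.** Protocol section 5 says the SAEs seen so far were similar on CER-001 and placebo, "with the possible exception of infusion reactions which occurred more frequently with CER-001 and may occur more frequently at higher doses". Protocol 3.3.2 makes the same exception for the earlier trial in acute coronary syndrome and says what is meant: "with the possible exception of infusion reactions (drug hypersensitivity reactions, anaphylaxis, and adverse drug reactions"). Protocol 11.6 adds: "Other AEs that may be anticipated are local injection site reactions and allergic responses". It then describes them by symptom: "These reactions may include one or more of the following symptoms: wheezing, eye itching, eye swelling, facial swelling, rash", and so on to diarrhea. For the other anticipated effects, liver enzymes and red cell indices, the same section says "although these have not been observed with single or multiple human doses at a rate higher than that observed with placebo".

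**The planned safety output.** SAP 7.5.1 has three layers:
- an overview of patients with any, serious, severe, related or fatal events, and events that led to a dose change or discontinuation;
- term-level tables: "TEAEs will also be tabulated by System Organ Class (SOC) and PT", split by seriousness, severity and relationship, and repeated for the induction and post-induction periods;
- one medically defined group: "All PT with HLGT = Coronary artery disorders will be described in the same way in a separate table".

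Onset relative to the last dose is an item only in the individual listings of deaths, other SAEs and events that changed dosing.

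**Infusions.** SAP 7.3.2 summarises the percentage of planned infusions given in full by randomized group, on the mITT population. For infusions of unusual duration or incomplete volume, "a by-patient listing will be produced for each patient who verified for at least one visit".

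**The concern.** Safety and tolerability over 24 weeks is a primary objective (protocol 4.1, SAP 1.1), and each patient is scheduled for 29 infusions. The obvious tolerability question is how many patients in each arm had an infusion or hypersensitivity reaction, and no planned table answers it. The overview rows mix all event types, and the term-level rows may divide one kind of reaction among several preferred terms and organ classes. Neither document defines a reaction category, a term list or an onset window.

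The SAP already accepts that a medical concept may need its own group, because it builds one for coronary events. It builds none for the risk on which the protocol reports an excess. If the count is assembled only after unblinding, it becomes an unplanned analysis under the SAP's own introduction, with the terms open to choice.

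**Working it through.** **Is there a plan figure to reproduce?** No. Neither document states a reaction rate or a safety precision target. The rates below are assumptions, shown as a range.

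**Inputs**
- 30 patients randomized 2:1 (protocol 6.4): 30 × 2/3 = 20 CER-001 and 30 × 1/3 = 10 placebo.
- Symptoms listed in protocol 11.6, by count: 21.
- Assumed share of CER-001 patients who react: 10%, 20% or 30%.
- Assumed number *k* of preferred terms used: 3, 6, 10 or 21, with each reacting patient placed in one at random.

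**Step 1. Which planned row isolates the reactions?**

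| Planned output (SAP) | Reaction count per arm? |
|---|---|
| Overview: any, serious, severe, fatal, leading to dose change | No, all event types together |
| Overview: related events | No, all types together, and it rests on the investigator's attribution |
| Organ class and preferred term tables, with splits | Only if all reactions share one term |
| Coronary group | Not this concept |
| Listings of deaths, SAEs and dose-changing events | No, individual data |
| Compliance (7.3.2) | No, full infusions only, on the mITT population |

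Recurrent events with the same preferred term count once per patient, so repeat reactions over 29 infusions do not show in those counts either.

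**Step 2. How thin could the rows be?** Expected patients per row = 20 × rate / *k*. At 20%: 4/3 = 1.33, 4/6 = 0.67, 4/10 = 0.40, 4/21 = 0.19.

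Simulated chance that no preferred-term row holds more than one CER-001 patient, given at least two who react (20,000 runs per cell):

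| Rate | 3 terms | 6 terms | 10 terms | 21 terms |
|---|---|---|---|---|
| 10% | 38% | 61% | 74% | 86% |
| 20% | 15% | 33% | 49% | 70% |
| 30% | 3% | 12% | 24% | 48% |

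If every reaction is coded to one term, that row holds the full count and nothing is lost.

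**Step 3. What would a grouped row show?** Exact (Clopper-Pearson) 95% limits for *x* of *n*: lower = Beta(0.025; *x*, *n* − *x* + 1), upper = Beta(0.975; *x* + 1, *n* − *x*).
- CER-001: 2/20 = 10% (1.2% to 31.7%); 4/20 = 20% (5.7% to 43.7%); 6/20 = 30% (11.9% to 54.3%).
- Placebo: 0/10 = 0% (0% to 30.8%); 1/10 = 10% (0.3% to 44.5%).
- For comparison, a single-patient row: 1/20 = 5% (0.1% to 24.9%).

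Even 6/20 against 1/10 has widely overlapping intervals and a two-sided Fisher p of about 0.37.

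**The case against.** Much can be said for the plan as it stands.

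- **A reader might infer that events are tabulated only by organ class and preferred term.** They are not. The overview and the splits give more, and if reactions are judged at least possibly related, every reacting patient counts in the related-event row whatever the coding. This stands, but the row does not separate infusion reactions from other related events.
- **A reader might infer that reactions will scatter over single-patient rows.** The documents do not establish this. Protocol 11.4 prefers a diagnosis to a sign or symptom, and protocol 3.3.2 reports earlier reactions as diagnoses, so several could share a term. Six reacting patients landing in six different terms is extreme: *k*(*k* − 1)…(*k* − 5)/*k*⁶ gives 1.5% for 6 terms, 15% for 10 and 46% for 21. Splitting is possible, not certain.
- **A reader might infer that incomplete infusions are not compared by arm.** SAP 7.3.2 does compare them, through compliance. What stands is narrower. Compliance pools partial with missed infusions and uses the mITT population, which omits treated patients without follow-up imaging. Slowed infusions are only listed.
- **The protocol's wording is qualified.** The sentence concerns SAEs and calls infusion reactions a possible exception. Serious reactions, and those that change dosing, do get listings with timing, and SAP 7.7 lists all collected data. But a listing is not a rate per arm.
- **A loose definition could do harm.** Taking any symptom of protocol 11.6 on the infusion day or the next would cover 2 of 7 days under weekly dosing and 2 of 14 under two-weekly dosing. Headache, nausea or fatigue from other causes would enter both arms. This stands and shapes the fix.
- **The monitoring board has its own SAP** (SAP section 9), which was not available for this review. It may group such events, but it does not govern the final report.

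**Conclusion.** The gap is real and limited. The protocol singles out infusion reactions, safety is a primary objective, and no planned table gives patients per arm with at least one such reaction. The existing rows either mix these reactions with other events or may divide them among several terms. How much is lost depends on an unknown rate and on site coding: from nothing, if one term is used, to a 70% chance of no row above one patient at a 20% rate spread over 21 terms.

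It would go too far to say that the plan hides a clearly raised risk, or that a grouped row would reveal one. With about 20 and 10 patients, 30% against 10% would still be inconclusive, and safety is analysed descriptively by design (protocol 12.3.2). The gain is an interpretable rate and interval per arm, defined before unblinding. This is a cheap improvement worth making. It is not a flaw that invalidates the safety analysis.

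**What to change.** Add to the SAP 7.5.1 overview, with its own table as for coronary events, a pre-specified infusion/hypersensitivity reaction group. Fix the term list and the onset window at the blinded data review.

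- **Core definition:** hypersensitivity, anaphylaxis and infusion- or injection-site reaction terms with onset in the fixed window after an infusion.
- **Broad definition, shown separately:** the core plus the unspecific symptoms of protocol 11.6 in the same window.
- **Report by arm, on the safety population:** patients with at least one reaction, with exact 95% CIs; the proportion of infusions with a reaction; and the proportion of infusions slowed or not fully given, with partial infusions separated from missed ones. Use the severity and period splits already planned. Infusions are clustered within patients, so give the infusion-level proportions without a simple binomial interval.
- **Interpretation:** state that the results are descriptive.

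The cost is one extra table and an agreed term list. Event dates, infusion start and stop times, volumes and reasons for altered duration are already collected (protocol 11.4, SAP 7.3.2). The downside is that the rate depends on the definition, which is why it must be fixed before unblinding. No treatment or assessment changes.

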### **8.14 Safety Assessments**

#### **8.14.1 Primary safety parameter**

The primary safety parameter will be to:

- Evaluate safety and tolerability of CER-001 administered for 24 weeks

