#### **8.14.2 Secondary safety parameters**

The secondary safety parameter will be to:

- Evaluate safety and tolerability of CER-001 administered for 48 weeks

Safety parameters will also be evaluated as secondary endpoints and will include:

- Incidence and severity of AEs from routine monitoring
- Incidence of abnormalities and changes from baseline in clinical laboratory parameters from testing of blood and urine, including antibody development

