1.1 Primary objectives

The primary objectives of the study are:

- To evaluate the effect of 24 week treatment with CER-001 on carotid Mean Vessel Wall Area (MVWA) as compared to placebo using 3T Magnetic Resonance Imaging (3T-MRI);
- To evaluate the safety and tolerability of CER-001 administered for 24 weeks.

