1.2 Secondary objectives

The secondary objectives of the study are:

- To evaluate the effect of 8 week and 48 week treatment with CER-001 on carotid artery MVWA as compared to placebo using 3T-MRI;
- To evaluate the effect of 8 week, 24 week and 48 week treatment with CER-001 on femoral artery MVWA as compared to placebo using 3T-MRI;
- To evaluate the effect of 24 week treatment with CER-001 in the target (plaque) to background (blood) ratio (TBR) from an index vessel (either right carotid or left carotid) based on the standardized ¹⁸FDG uptake measured with PET/CT.
- To evaluate safety and tolerability of 48 week treatment with CER-001.

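### Safety over 24 weeks is a primary objective, but no planned adverse event table covers W0 to W24

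*SAP*

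**What the plan says.** The primary safety objective in SAP 1.1 is "To evaluate the safety and tolerability of CER-001 administered for 24 weeks". The protocol gives the same objective in the Synopsis and section 4.1, and section 8.14.1 names it as the primary safety parameter: "Evaluate safety and tolerability of CER-001 administered for 24 weeks". The secondary version changes only the length of treatment. Protocol 8.14.2 has "Evaluate safety and tolerability of CER-001 administered for 48 weeks" and SAP 1.2 has "To evaluate safety and tolerability of 48 week treatment with CER-001".

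On AEs, SAP 7.5.1 sets out an overview and tables by system organ class and preferred term, seriousness, severity and relatedness. It then states: "The different analyses described above will be summarized overall, on the induction period and on the post-induction period". Post-induction is explained as "AEs that occurred during maintenance or extension phase". The induction rule is "Start date of TEAE < date of infusion at W10", and post-induction takes everything from that infusion on. An event is treatment-emergent "if AE onset date is between first infusion of CER-001 and last infusion of CER-001 + 28 days", or if it was present earlier and worsens on treatment.

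Protocol 12.3.2 tabulates AEs by treatment and sets no time window. The AE template in SAP 12.1 shows no period, and SAP 12.2 lists no further table in the text available.

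**The concern.** The primary and secondary safety objectives differ only in their time window, so the plan needs an AE summary for each. W24 is also the boundary between maintenance and extension (protocol 6.1.1) and the time of the primary efficacy endpoint. SAP 7.5.1 merges the phases on either side of that boundary.

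The planned tables therefore do not state the incidence, seriousness, severity or relatedness of AEs by arm over the period of the primary safety objective. The efficacy result would be given at 24 weeks, while the nearest AE table would run over 48 weeks of treatment plus follow-up. A 24-week AE table made after unblinding would be an unplanned analysis, which the SAP introduction says must be identified as such in the study report. AEs are also where protocol section 5 reports a possible difference from placebo, namely infusion reactions.

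**Working it through.** No stated figure is at issue, so the check compares windows and then asks whether the missing one can be derived.

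**Infusions (schedule in SAP 7.3.2)**
- Induction, W0 to W8: 9
- Maintenance, W10 to W24: 8
- Extension, W26 to W48: 12
- Due by W24: 9 + 8 = 17. Total: 17 + 12 = 29. Both agree with the SAP's denominators.
- Post-induction: 8 + 12 = 20, of which 12/20 = 60% come after W24.
- Share of the 24-week infusions that falls in induction: 9/17 = 53%.

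**Nominal calendar windows**

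Here CER-001 in the treatment-emergent rule is read as study drug, so that placebo patients also have a window, and follow-up ends at W48 + 28 days = W52.

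| SAP summary | Window | Part inside W0 to W24 |
|---|---|---|
| Induction | W0 to W10 | 10 weeks, which is 10/24 = 42% of the target period |
| Post-induction | W10 to W52 (42 weeks) | 14/42 = 33% of the window |
| Overall | W0 to W52 (52 weeks) | 24/52 = 46% of the window |

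The rules state no upper limit at W48. If open-label infusions to W72 were counted, the window would close at W76, and the last two shares would fall to 14/66 = 21% and 24/76 = 32%.

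**Can the W0 to W24 count be derived?**

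Let I, M and E be the sets of patients with at least one event in induction, maintenance and extension. The plan gives |I|, |M ∪ E| and |I ∪ M ∪ E|. The objective needs |I ∪ M|. The planned tables fix only the bounds

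|I| ≤ |I ∪ M| ≤ |I ∪ M ∪ E|,

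so the 24-week count can lie anywhere between the induction count and the overall count. Splitting post-induction into M and E would not settle it either, because |I| + |M| counts a patient with events in both periods twice. A cumulative table is needed.

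Severity has a further problem. SAP 7.5.1 counts recurring events with the same preferred term once per patient, at the worst intensity. In the overall table, an event before W24 can therefore carry a grade reached only after W24.

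**What the SAP does report at W24**
- Compliance (7.3.2)
- Completion of maintenance, and discontinuations and withdrawals with reasons at each visit (6.3)
- Vital signs, ECG and physical examination (7.5.2)
- Laboratory values (7.5.3)

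AEs are the safety data with no W24 cut.

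**The case against.** The strongest reply is that the protocol places AE incidence and severity under secondary safety parameters (Synopsis and 8.14.2), while 8.14.1 names no measure for the primary one. On that reading no 24-week AE table was promised. The classification is as stated, but the reply does not remove the gap. Tolerability over 24 weeks would ordinarily include AEs, and without them the primary safety parameter has no defined measure.

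The second reply is that W24 examinations, laboratory results and by-visit discontinuations already serve the objective. They do in part. A reader might infer that the primary and secondary safety objectives rest on the same output throughout; that is true only of the AE tables.

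Third, a reader might infer that 24-week AE results would be unobtainable. The documents do not support that. SAP 7.5.1 plans individual listings of deaths, other serious events and events leading to dose reduction or discontinuation, and SAP 7.7 plans listings of all collected data. With 30 planned patients, a count could be made later. It would be unplanned, not impossible.

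Fourth, a reader might infer that SAP section 10 conceals a departure from the protocol. It does not, because protocol 12.3.2 set no AE window and there was nothing to depart from.

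Finally, the infusion shares are not event counts and show no bias between arms. The overall table contains every early treatment-emergent event, and safety is analysed descriptively, so no error rate is affected. All of this stands and limits the point to reporting.

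**Conclusion.** The point holds as a gap in the planned AE tables. The period rule in SAP 7.5.1 does not match the primary safety objective: no AE summary covers W0 to W24, and the three planned ones leave that count undetermined between the induction and overall counts. In infusions, 60% of post-induction lies after W24, and induction covers 53% of what is due by W24.

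No data are lost and no test is affected. It should still be corrected, because the objective is primary, the remedy is cheap, and a window chosen after unblinding is weaker evidence than one fixed beforehand. The conclusion assumes that AEs are part of safety and tolerability over 24 weeks, and that SAP 7.5.1 is the governing specification, since SAP 12.2 lists no additional AE tables in the text available.

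**What to change.** Before unblinding, add to SAP 7.5.1 a cumulative period called through W24:
- **Events:** all treatment-emergent AEs as the SAP defines them, including pre-existing AEs that worsen on treatment, with onset or worsening before the W26 infusion. This follows the SAP's own pattern, in which induction closes at the first infusion of the next phase. The label should explain that the window nominally reaches W26.
- **W26 infusion not given:** use the scheduled W26 date (26 × 7 = 182 days after the first infusion).
- **Treatment stopped earlier:** use the last infusion + 28 days if that is sooner. For example, a last infusion at W20 closes the window at W24. A last infusion at W24 would give W28, so the scheduled W26 date applies.
- **Output:** the AE overview and the tables by system organ class and preferred term, seriousness, severity and relatedness, by arm, named as the primary safety analysis.
- **Secondary analysis:** keep the 48-week tables, stated to be confined to the double-blind phase.

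The cost is one period definition and one more run of tables already planned. No new data are needed.
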